DOLF studies in Liberia have provided some of the most complete data on the impact of community MDA regimens for LF and other NTDs. These studies have shown that 3 years of MDA had significant impacts on LF, STH and onchocerciasis prevalence in Liberia and other study sites. However, three years of MDA was not sufficient to meet elimination targets for those infections. An additional survey in the Maryland district will provide further data on the rate of decline of filarial antigenemia prevalence following MDA in Africa and on the effects of additional rounds of MDA on onchocerciasis and on STH prevalence and intensities. Three of these study areas had very high STH prevalence at baseline (two in Liberia and one in DRC), and continuation of measuring the impact MDA through 7 years after initiation will prepare these areas as potential sites for later studies of the efficacy of school-based deworming or other maintenance strategies to prevent the rebound of STH following cessation of MDA for LF.

In the last three years, annual MDA has been administered by the the NTD team of the Ministry of Health (MOH) in Lofa and by MOH/COUNTDOWN in Maryland. At a follow-up visit in 2019 by Liberian DOLF team members, all 16 study villages had received MDA. In Lofa County, MDA was conducted through the MOH alone, and the DOLF team recorded that not all of the 26 study villages in Lofa received MDA in 2018.

The proposed additional survey will provide data on long-term impact of MDA and support endgame research to understand how many rounds of MDA are needed to achieve elimination of LF and oncho and control of STH infections. The elimination targets for LF are <2% prevalence of antigen (assessed with FTS) and <1% prevalence of microfilaria (assessed with thick blood smear). The elimination target for onchocerciasis is <5% microfilaria in the skin (assessed by skin snip). The proposed survey will determine if these targets have been reached, and will answer the question of how many additional rounds of MDA are needed to achieve elimination targets. The answer to this question is critical for global elimination programs and may inform global policies.

10. 2.3 Potential Risks and Benefits / Potential Risks

Immediate risks

11. 2.3.1 Potential Risks

This research includes risks associated with collection of blood by finger prick and of skin snips (superficial skin biopsies collected by corneoscleral biopsy punch).

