Likely	Collection of blood and skin snips causes minor pain.
Less Likely	Collection of blood can cause a bruise, bleeding or infection at the collection site. To minimize risks, sterile disposable lancets will be used for blood collection. Blood will be collected after disinfecting the skin with alcohol. Subjects will be instructed to apply pressure to finger prick sites to minimize bleeding and hematoma formation. The amount of blood being collected (less than 1 ml) is not enough to cause anemia.

Collection of skin snips can cause a bruise, bleeding or infection at the collection site.

To minimize risks, skin snips will be collected after disinfecting the skin with alcohol using a sterile skin snip punch. Skin snip punches will be cleaned and soaked in 4% Mucocit-P for 5 minutes and then rinsed with 70% ethanol between subjects. Subjects will be instructed to apply pressure to skin snip sites for two minutes and to keep these areas clean.

There are no risks associated with collection of stool or urine samples.

Long range risks: None

- *Rationale for the necessity of such risks:* Blood and skin snips are required for diagnosis of filarial infection. Procedures in this project meet the definition of “minimal risk”. Stool and urine samples are needed for diagnosis of other STH and schistosomiasis infections.
- *Alternative data gathering procedures that have been considered or will be considered:* None. Blood and skin snips are needed for diagnosing filarial infections (microfilariae) which are the subject of this project.
- *Why the value of the information to be gained outweighs the risks involved.* The potential benefits to individuals, society and science are considerable. The risks are minimal.

12. 2.3.2 Known Potential Benefits

- To subjects:
The study will screen participants for parasitic infections and refer infected subjects for treatment at their local government health center. We will also provide data on infection rates to district health officials. This information will help the Liberian Ministry of Health to plan public health programs for villages where our study subjects live.
- To society:
Participation will provide information on the impact of MDA on filarial and STH infections that affect the public health in the community.

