3 OBJECTIVES

To conduct population-based field studies to determine the relative cost and efficacy of annual vs. semiannual MDA for control and elimination of onchocerciasis and lymphatic filariasis.

1. We will test the hypothesis that twice annual MDA is superior to annual MDA for eliminating lymphatic filariasis.
2. We will test the hypothesis that twice annual MDA is superior to annual MDA for controlling soil transmitted helminth infections and onchocerciasis.
3. ***Following conclusive results on the first objectives that annual MDA is as effective as semiannual MDA for LF, oncho and STH, we will conduct an additional survey to determine long term (7 year) impact of continued MDA on onchocerciasis, LF, and STH in two areas.***

13. 4 STUDY DESIGN

(Please read this section together with Section 5, “Study Population”)

The project is comprised of repeated annual cross-sectional surveys in sentinel communities before and after initiation of mass drug administration for LF. MDA (standard regimens recommended by WHO) will be provided by government health officials. Data collection will include demographic data, history of lymphedema, scrotal swelling (hydrocele), acute filarial fever or adenolymphangitis, prior treatment for LF. Information on the presence of onchocercal nodules as well as on onchocercal skin and eye disease will be also recorded. Nodules will be assessed by superficial palpation. Blood samples will be collected from systematically sampled households. Blood will be tested for filarial antigenemia with one or more of the following: the BinaxNow Filariasis card test (also known as ICT), the Alere Filariasis Test Strip, and the TropBio test. Blood will also be tested for onchocerciasis (serology testing). Blood from persons with positive filarial antigen tests will also be tested for microfilaremia (*W. bancrofti* MF in the blood, see Section 6 below for methods). Two skin snips will be examined for microfilaridermia (*O. volvulus* MF in the skin, see Section 6 below for methods). Stool examinations will be performed for diagnosis of STH infections and schistosomiasis (*S. mansoni*), and urine will be tested for *S. hematobium*. *Note that not all tests will be performed on all samples (blood, stool and/or urine).*

Safety oversight: Study personnel will monitor subjects for adverse events related to blood collection. No medical monitor or DSMB is needed for this minimal risk, non-intervention study.

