Onchocerca volvulus infection- nodule palpation, skin snips and oncho serology: We are using these tests as measures of onchocerciasis endemicity. Due to the presence of deep nodules which cannot be assessed by superficial palpation, nodule data provide only an inaccurate estimate of endemicity. However, this method is used for rapid mapping of onchocerciasis and will be included. The assessment of MF in the skin is a more reliable measure of endemicity in areas with no community directed treatment using ivermectin. After treatment the presence of MF gives valuable information about the MF available for transmission. Two skin snips from skin over the iliac crest will be taken from subjects the same subjects who are tested for filariasis as described above. Blood collected for *W. bancrofti* antigen detection (see above) will be also used for onchocerciasis serology.

Stool examination for infection with STH and schistosomiasis. We will examine stool samples of the study population mentioned above for the presence and the density of STH eggs and *S. mansoni* eggs. We will use the FLOTAC and Kato-Katz (KK) methods to examine a single stool sample from each subject. These methods have excellent sensitivity and will provide accurate data on both the prevalence and intensity of infection. We will use community egg loads as a main indicator which combines both prevalence and density of infection and we target 95% reduction for each species. The Liberian MOH has agreed to provide Praziquantel to communities shown by our study to have high rates of schistosomiasis.

Urine examination for infection with *Schistosoma hematobium* We will examine urine samples by microscopy for the presence and the density of *S. hematobium* eggs. The Liberian MOH has agreed to provide Praziquantel to communities shown by our study to have high rates of schistosomiasis.

Continuation Activities (2019)

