With 4 years of annual cross-sectional surveys conducted by DOLF researcher and completed in both Maryland (last survey in 2016) and Lofa (last survey in 2017), we plan to conduct an additional one-time cross-sectional survey in the Harper site in Maryland district in 2019 and in Lofa (Foya & Kolahun Districts) in 2020 to measure the long-term impact of MDA on *W. bancrofti* (lymphatic filariasis), *O. volvulus* (onchocerciasis) and on STH infection parameters following these cumulative 7-9 rounds of MDA. Since the last DOLF surveys, there have been a total of 3 annual rounds of MDA in both areas.

The study will recruit 2,500 participants in the Maryland area villages and 3,200 in the Lofa area villages. The proposed activities will comprise of identical survey methods as previously conducted surveys in both study areas. The survey includes:

- ***Stool sample collection with Kato Katz analysis for STH infections,***
- ***Blood collection by finger prick during the day with analysis by FTS and thick blood smear for detection of *W. bancrofti* antigen and microfilaria (respectively) in the blood (TropBio antigen test and Binax Now card tests will not be used as they were found to be inferior to the Alere Test Strip (FTS))***
- ***Skin snips for detection of *O. volvulus* microfilaria in the skin***

As a final note, we will not provide MDA as part of this research, but we will share our findings to the MOH and others to support their decision-making for MDA continuation or cessation. We will publish the findings to support global policy decision making.

STUDY POPULATIONS

Description of human subject involvement in research:

We will perform repeated annual cross-sectional surveys in study communities. Eligibility: This project will study people who live in communities that are endemic or have been endemic at the beginning of the study for lymphatic filariasis (LF) and onchocerciasis (oncho). The LF endemicity rate (MF rate) should at the study begin should be about 10% and there should have been no MDA in area immediately prior to study begin. The prevalence of oncho is secondary, but should be at least 5% nodule rate or 10% skin MF. ***Eligibility criteria will remain the same in the continuation surveys in both areas.***

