20. 7.2 Sample Size Considerations

Except as otherwise noted, all sample sizes in this protocol were calculated using a binomial power calculator (using alpha = .05, two-tailed tests, and power = .80). These sample sizes were chosen to provide confidence that measured prevalence rates will be below specified limits based on assumptions regarding true prevalence rates. The sample size analysis considered various contingencies to assess robustness of the sample size estimates (see Appendix).

Note: Sample size considerations for community surveys for demonstrating that prevalence rates are below pre-defined targets for antigenemia, microfilaremia, microfiladermia, schistosomiasis, and STH infections are provided in Section 4, above, and this is not repeated here.

21. 7.3 Participant Enrollment and Follow-Up

This project aims to enroll at least 3,200 subjects per year in Foya District and 2,000 subjects per year in Maryland County. Study areas will have cluster surveys of approximately 400-500 people per 4 sentinel site (4 sites each in the annual and semiannual MDA areas). The community/household surveys are cross-sectional with no follow-up planned.

22. 7.4 Analysis Plan

The following outcome variables will be collected and treated as binary variables: Microfilaremia, microfiladermia, filarial antigenemia and antibody, and stool/urine parasites (separate analyses for *Ascaris*, *Trichuris*, schistosomes, and Hookworm). Microfilaria counts (recorded as MF/60 μ l blood), microfiladermia counts as MF/mg skin, nodules as nodules per person, and stool egg counts for each species (recorded as eggs/gram of feces or eggs/ml urine) will be taken as count variables.

Data will also be collected for demographic characteristics and covariates including age, gender, and history of lymphedema, scrotal swelling (hydrocele), and prior treatment for LF. For demographic characteristics variables, descriptive statistics will be examined for the individuals who participate in the trials by sentinel site (village) and over years of observation. Frequency will

be tabulated for categorical variables. Descriptive statistics (mean, median, range and standard deviation) will be obtained for continuous variables.

Impact of MDA on study outcome measures

1. Testing the primary hypothesis

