With microfilaria (per 60 μ l of blood) measured as counts, we will display mean counts of microfilaria across the four sentinel sites from each treatment zone (annual vs. twice annual MDA) over years of observation including the baseline. To accommodate zero counts in modeling, we will use Geometric mean intensity (GMI) of circulating microfilaria. GMI is calculated as $\text{antilog}[(\sum \log(x+1))/n] - 1$, where x is the number of microfilaria per 60 mm^3 of blood and n is number of subjects. A generalized linear mixed model (GLMM) (implemented in PROC GLIMMIX) will be used to account for correlation of observations resulted from clustering. CONTRAST statements will be used to test the significance of differences in GMI of antigenemia between the two treatment

regimens at each year of observation. The resulting estimates of GMI will be presented with 95% confidence interval. All statistical tests will be two-sided at a significance level of 0.05, but one-sided p-value will be reported according to the hypothesis. Similar analytic models will be done for community Mf loads, community *O. volvulus* Mf load, and for community egg loads for each of three intestinal worm species.

The cost analysis comparing the two treatment regimens will be conducted by [name] of the George Washington University School of Public Health and Health Services. The model will also allow cost effectiveness analysis when combined with the efficacy analysis.

2. Testing secondary hypothesis

The secondary hypothesis is that twice annual MDA is superior to annual MDA for controlling STH and onchocerciasis in the Foya district. The primary endpoint for assessing the impact of MDA on STH infections is community egg load (average stool egg count per species). The primary endpoint for onchocerciasis will be Mf prevalence by skin snip. We will also compare community Mf loads for onchocerciasis. The analysis strategy for these end points is the same for microfilaria count in testing the primary hypothesis.

Adverse event

Since this is a minimal risk and nonintervention study, adverse events are not expected to be an issue. However, subjects will be monitored for adverse events related to blood collection. Proportion of subjects with an adverse event will be tabulated with 95% confidence interval for each sentinel site at each year of observation.

Treatment coverage rate

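### Adverse event monitoring is stated only for blood collection, although skin snips are the second named source of risk, so the adverse event proportion would probably under-count snip events

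*Combined protocol and SAP*

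**What the plan says.** On risk, Section 2.3.1 opens with "This research includes risks associated with collection of blood by finger prick and of skin snips". Its risk table then gives the harms for each procedure. For the biopsy it states: "Collection of skin snips can cause a bruise, bleeding or infection at the collection site". The same three harms are listed for blood collection. The table also gives precautions for each procedure: disposable lancets for blood, and for snips a sterile punch that is cleaned, soaked and rinsed between subjects, with pressure on the site and advice to keep it clean.

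On exposure, Section 4 says "Two skin snips from skin over the iliac crest will be taken from subjects", namely those tested for filariasis. The continuation activities keep the procedure. Their list of survey components includes "Skin snips for detection of" *O. volvulus* microfilariae.

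On monitoring, the safety oversight paragraph of Section 4 says "Study personnel will monitor subjects for adverse events related to blood collection", and adds that neither a medical monitor nor a DSMB is needed. Section 7.4 repeats the limit: "subjects will be monitored for adverse events related to blood collection". Its next sentence sets the analysis: "Proportion of subjects with an adverse event will be tabulated with 95% confidence interval for each sentinel site at each year of observation".

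On timing, Section 4 puts participation at one day, and Section 7.3 says "The community/household surveys are cross-sectional with no follow-up planned".

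**The concern.** The protocol names two procedures that can harm a participant and provides for monitoring one of them. The one left out is a biopsy taken twice per person with punches that are reprocessed and reused. It is also central to the study, because skin-snip microfilaria prevalence is the primary onchocerciasis endpoint in Section 7.4.

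Two things are at stake. The first is oversight: with no medical monitor or DSMB, observation by study personnel is the only safety monitoring described. The second is the meaning of the reported figure. A proportion of subjects with an adverse event, given by site and year with a confidence interval, will be read as covering all study procedures. If staff were told to look for events from one procedure only, a low figure says little about the other.

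**Working it through.** The plan states no adverse event rate and no safety sample size, so there is no figure to reproduce. The check is a comparison of the relevant text, followed by the size of the group affected.

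**1. The passages side by side**

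| Element | Blood collection | Skin snips |
|---|---|---|
| Named as a source of risk (2.3.1) | Yes | Yes |
| Bruise, bleeding, infection listed (2.3.1) | Yes | Yes |
| Precautions given (2.3.1) | Yes | Yes |
| Monitoring in safety oversight (4) | Yes | Not mentioned |
| Monitoring in analysis plan (7.4) | Yes | Not mentioned |
| Tabulation (7.4) | No procedure named | No procedure named |

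The restriction appears in two separate sections, so a single slip of wording is an unlikely explanation. The laboratory procedures in Appendix A do not mention adverse events, and the available part of Appendix B says only that field staff will be trained.

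**2. What the tabulated proportion would measure**

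Let *b* be the proportion of subjects with a blood-collection event, *s* the proportion with a snip event, and *c* the share of snip events that reach the record without active monitoring. Ignoring people with both, and taking blood events as fully recorded:

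- reported proportion ≈ *b* + *c·s*
- true proportion ≈ *b* + *s*
- shortfall ≈ (1 − *c*)·*s*

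If every snip event is volunteered and recorded (*c* = 1), nothing is lost. If none is (*c* = 0), all of *s* is lost. The documents give neither *c* nor *s*. They support the direction of the error but not its size.

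**3. People and procedures affected**

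- Continuation surveys: 2,500 (Maryland) + 3,200 (Lofa) = 5,700 participants.
- Two snips each: 5,700 × 2 = 11,400 snips.

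Both are upper limits that assume everyone is snipped. Section 4 notes that not all tests will be done on all samples, although that note refers to blood, stool and urine.

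**4. How a zero count would read**

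Section 7.3 plans about 400 to 500 people per sentinel site. With no events among *n* subjects, the exact two-sided 95% upper limit is 1 − 0.025^(1/*n*):

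- *n* = 400: 1 − 0.025^(1/400) = 0.0092, about 0.9%
- *n* = 500: 1 − 0.025^(1/500) = 0.0074, about 0.7%

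A reader would take such a limit to bound harm from all study procedures. Under the monitoring as worded, it would properly bound blood-collection events only.

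**The case against.** The strongest reply is that the tabulation sentence in Section 7.4 is generic. It counts subjects with an adverse event and names no procedure, so a snip event that was seen or reported would fit it. This stands. A reader might infer that snip events are excluded from the table, or that they are neither monitored nor counted. The text supports only that active monitoring is stated for blood collection and that the status of snip events in the table is unclear.

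A reader might also apply an assumed event rate to the annual enrolment of about 5,200 and quote a yearly number of uncounted people. The documents do not support that. They give no rate, and the continuation section says the annual surveys are completed. What remains is two one-time surveys.

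A third reply is that the study is classed as minimal risk and that snip-specific precautions are already in Section 2.3.1. Both are true and they limit the importance of the point. They do not explain the asymmetry, because the classification covers both procedures. Nor does the gap undermine that classification: it is a prior judgement about the procedures, and nothing says the adverse event table will be used to justify it.

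Rewording would also recover mainly same-day bruising and bleeding. With one-day participation and no follow-up, a later site infection could be missed after either procedure. This stands too and belongs in the report.

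Finally, field procedures are only partly available in the text, so the absence of provision for snip events is established only for what can be read.

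**Conclusion.** The point holds as a gap between the stated risks and the stated monitoring. Sections 4 and 7.4 provide for monitoring of blood-collection events only, while Section 2.3.1 names skin snips as a second source of the same three harms. The adverse event proportion would probably under-count snip events.

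The gap bears on up to 5,700 participants and 11,400 snips in the continuation surveys. The number of events lost is unknown. The conclusion assumes that staff follow the monitoring sentences as written and that no unseen field procedure fills the gap.

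No hypothesis, efficacy endpoint or sample size is affected. The change is worth making because it is cheap and concerns the only safety monitoring that the protocol describes.

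**What to change.** 1. Reconcile Sections 4 and 7.4 with Section 2.3.1 by adding *or skin snips* after *blood collection* in both monitoring sentences.
2. Record which procedure each event relates to.
3. Report the proportion with its 95% confidence interval, by site and year, and state that it covers both procedures. A breakdown by procedure is optional, since counts per site may be small.
4. State in the report that, with one-day participation and no follow-up, delayed events such as site infection may be missed after either procedure.
5. For surveys already completed, label the adverse event proportion as actively monitored for blood collection only.

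The cost is a few words in two sections and a small amount of extra recording. The documents describe no adverse event form, so the recording effort is an assumption. No extra visit is implied, and the change does not by itself recover delayed events.
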